#### 4. Sterilization:

Sterilize the handpiece using a steam sterilization cycle. The sterilization instructions provided in Table 1 below have been validated by Alcon Laboratories, Inc. as being CAPABLE of sterilizing the Infiniti® Ozil and U/S Handpieces for re-use. It remains the responsibility of the processor to ensure that the processing as actually performed using equipment, materials and personnel in the facility achieve the desired result. This requires verification and routine monitoring of the process. Likewise any deviation by the processor from the instructions provided should be properly evaluated for effectiveness and potential adverse consequences. Please refer to nationally recognized standards, or to your facility's standard procedures.

Note: Due to the potential for the accumulation of particulate and bioburden residues in the sterilizer water reservoirs, it is the surgical facility's responsibility to properly maintain the equipment and their associated filters to ensure the introduction of steam into the Handpiece is contaminant free at levels acceptable per the surgical facility's requirements.

Table 1 - STERILIZATION TEMPERATURES AND TIME SETTINGS

STERILIZER TYPE	PULSES	CONFIGURATION	MINIMUMTEMPERATURE	MINIMUM EXPOSURE TIME (MINUTES)
Gravity Displacement	N/A	Wrapped	132° C (270° F)	18
Gravity Displacement	N/A	Unwrapped	132° C (270°F)	8
Pulsing Prevacuum	4	Unwrapped	132° C (270° F)	4
Pulsing Prevacuum	4	Wrapped	134° C (273°F)	5
Pulsing Prevacuum (four negative and four positive pulses)	4	Wrapped	134-137°C (273-279°F)	3

Note: This product has been validated to perform reliably after steam sterilization at 134°C (273°F) for 18 minutes (prevacuum, wrapped).

- After transport to the driving console for the next use, refer to your driving console Operator's Manual for proper surgical setup.
- Refer to Alcon's Pack/Tip Directions for Use for proper assembly of the tip to the Handpiece.
   There are not specific limits for the time or conditions of storage.
- 8. References:

\*EN ISO 17664: Sterilization of medical devices - Information to be provided by the manufacturer for the processing of resterilizable medical devices.

Definitions for symbols that may appear on product labels:

	SEE DIRECTIONS FOR USE	 	MANUFACTURER	SN / SN	SERIAL NUMBER
葱	DOES NOT CONTAIN LATEX OR DRY NATURAL RUBBER	M	DATE OF MANUFACTURE	REF / REF	CATALOG NUMBER

**Short Title: Statistical
Analysis Plan CTU424-P001**

Full Title:

**Statistical Analysis Plan
CTU424-P001 / NCT02502526**

Protocol Title: Comparison of Cumulative Dissipated Energy (CDE) and BSS Fluid used with the Centurion® with the 45° Balanced U/S tip vs the Centurion® with Mini Flared Kelman U/S tip vs the Infiniti® with Mini Flared Kelman U/S tip on Hard Lenses

Project Number: CTU424-P001

Reference Number:

Protocol TDOC Number: TDOC-0050176

Author:

Approvals:

See last page for electronic approvals.

Job Notes:

This is the second revision (Version 3.0) of the Statistical Analysis Plan. Revisions were made to correct the calculation for  and to provide clarification on how endothelial cell density data would be analyzed.

Executive Summary:**Key Objective:**

The key objective is to demonstrate that the Centurion® Vision System used with the 45° Balanced tip will result in less Cumulative Dissipated Energy (CDE) than the Infiniti® Vision System used with the 45° Mini-Flared Kelman (MFK) tip during cataract extraction surgery via phacoemulsification of cataract grades NII- NIV (LOCSII).

Decision Criteria for Study Success:

The primary performance endpoint is CDE, compared between Centurion® with the 45° Balanced tip and Infiniti® with the MFK tip.

The difference in CDE between these two groups will be examined via an analysis of covariance (ANCOVA) model adjusting for site and baseline opacity grade. The difference in least squares (LS) means will be calculated, along with a one-sided p-value. If this p-value is less than 0.05, it will be concluded that the CDE for Centurion® with the 45° Balanced MFK tip is statistically significantly less than the CDE for Infiniti® with the MFK tip.

Table of Contents

1	Study Objectives and Design.....	5
1.1	Study Objectives.....	5
1.2	Study Description.....	7
1.3	Randomization.....	8
1.4	Masking	8
1.5	Interim Analysis	9
2	Analysis Sets.....	9
2.1	Performance Analysis Sets	9
2.2	Safety Analysis Set.....	9
2.3	Pharmacokinetic Analysis Set	9
3	Subject Characteristics and Study Conduct Summaries.....	9
4	Performance Analysis Strategy.....	10
4.1	Performance Endpoints	10
4.2	Performance Hypotheses	10
4.2.1	Hypothesis for the Primary Endpoint	10
4.2.2	Hypothesis for the Secondary Endpoints	11
4.3	Statistical Methods for Performance Analyses.....	12
4.3.1	Primary Performance Endpoint	12
4.3.2	Secondary Performance Endpoints	12
4.4	Multiplicity Strategy.....	12

1.1 Study Objectives

PRIMARY OBJECTIVE

Demonstrate that the Centurion® Vision System used with the 45° Balanced tip will result in less Cumulative Dissipated Energy (CDE) than the Infiniti® Vision System used with the 45° Mini-Flared Kelman (MFK) tip during cataract extraction surgery via phacoemulsification of cataract grades NII- NIV (LOCSII).

SECONDARY OBJECTIVES

- 1). Demonstrate that the Centurion® Vision System used with the 45° Balanced tip will result in less CDE than the Centurion® Vision System used with the 45° MFK tip during cataract extraction surgery via phacoemulsification of cataract grades NII-NIV (LOCSII).
- 2). Demonstrate that the Centurion® Vision System used with the 45° Balanced tip will result in less BSS Fluid Used than the Infiniti® Vision System used with the 45° MFK tip during cataract extraction surgery via phacoemulsification of cataract grades NII-NIV (LOCSII).
- 3). Demonstrate that the Centurion® Vision System used with the 45° MFK tip will result in less BSS Fluid Used than the Infiniti® Vision System used with the 45° MFK tip during cataract extraction surgery via phacoemulsification of cataract grades NII-NIV (LOCSII).
- 4). Demonstrate that the Centurion® Vision System used with the 45° MFK tip will result in less CDE than the Infiniti® Vision System used with the 45° MFK tip during cataract extraction surgery via phacoemulsification of cataract grades NII- NIV (LOCSII).

1.2 Study Description

This is a prospective, parallel, randomized, multi-center, 3-arm, patient-masked clinical study to evaluate the Centurion® Vision System during cataract extraction surgery followed by posterior chamber IOL implantation in adult patients (≥ 21 years of age).

For this study, the softest lenses (LOCSII Opacities N0 and NI) will be excluded, leaving all lenses with LOCSII Opacities NII-NIV.

For each group, cataract surgery will be performed on eligible subjects randomized with an equal number in the following three arms, having their surgery performed with each configuration.

Eligible subjects will be assigned in 1:1:1 ratio in either of the three study arms:

- Arm 1: Centurion® Vision System, 45°Balanced tip¹
- Arm 2: Centurion® Vision System, 45°MFK tip¹
- Arm 3: Infiniti® Vision System, 45°MFK tip²

[figure not shown]
¹Used with INTREPID® Ultra Infusion Sleeve

² Used with Ultra infusion Sleeve

Approximately 177 subjects (59 in each group) will undergo unilateral cataract surgery in the study to reach a minimum of 159 evaluable subjects (53 in each group) at the conclusion of the 3-month post-operative visit. Subjects will be enrolled sequentially in consent date and time order. The expected duration of subject participation is approximately five months. The study includes 5 visits as outlined below.

Table 1 – 1 Visit Schedule

Examination	Visit	Time for Procedure
Pre-operative (Screening)	Visit 0	-60 to 0 days from study eye surgery
Operative (Day of Surgery)	Visit 00	Day 0
1-Day post-operative follow-up	Visit 1	Day 1
1-Week post-operative follow-up	Visit 2	Day 7 (+/- 2 days)
3-months post-operative follow-up	Visit 3	Day 90 (+/- 14 days)

Figure 1 – 1 Study Design

1.3 Randomization

A randomization list will be generated by Sponsor personnel who is not involved in the day-to-day conduct of the study, and who does not have contact with the study subjects, the site, or the Alcon employees who do have site contact.

Randomization should be completed within 2 working days prior to the date of surgery.

1.4 Masking

This is a subject-masked study and not observer-masked. Subjects will be masked to the treatment for the study eye. The surgeon (Investigator) is not masked to treatment as this is impossible with the medical devices studied here. Site personnel not participating in surgery and not requiring knowledge of randomization will be masked to the extent possible. Investigative sites will take all precautions necessary to ensure the subjects remain masked.

for the duration of the trial. It is encouraged that the Investigator take the opportunity to remind the subject that he/she will be masked for the duration of the trial.

1.5 Interim Analysis

No interim analyses are planned for this study.

2 Analysis Sets

Three analysis sets are defined: Safety, Intention-to-Treat (ITT) and Per-Protocol Set (PPS).

2.1 Performance Analysis Sets

The ITT set will include all subjects who are randomized in the study and receive procedure. The ITT set will be the primary analysis set for performance.

The PPS is a subset of ITT which excludes those who meet the critical deviation criteria as specified in the Deviations and Evaluability Plan. Supportive analysis of the primary and secondary endpoints will be conducted using PPS if the number of subjects excluded from PPS exceeds 5% of the ITT.

2.2 Safety Analysis Set

The safety analysis set will include all subjects exposed to any study procedures evaluated in this study. Safety data is to be collected for each subject beginning at the time of informed consent.

2.3 Pharmacokinetic Analysis Set

Not Applicable.

3 Subject Characteristics and Study Conduct Summaries

Demographic information (age, sex, ethnicity, and race) and baseline characteristics will be summarized overall and by procedure group on the ITT set.

Descriptive statistics for the crystalline lens assessment LOCS II scores, as well as ECD and [REDACTED] will be presented by procedure group and overall. In addition, frequency and percentage of subjects randomized at each investigational site will be presented by procedure group and overall. A listing showing the baseline crystalline lens assessment LOCS II scores will be provided.

4 Performance Analysis Strategy

4.1 Performance Endpoints

Primary Endpoint

- Cumulative Dissipated Energy (CDE)

Secondary Endpoints

- CDE and BSS fluid use

$$BSS\ Used = Incision\ Leakage\ Fluid + Aspiration\ Fluid\ Used$$
A large rectangular area of the page is completely blacked out, indicating that the original content has been redacted for security or privacy reasons.

Up to three specular microscopy images will be taken of the study eye at Visit 0 and Visit 3. The mean of the up to three values for endothelial cell density, coefficient of variation and percent hexagonal cells, rounded to one decimal place, will be used in the analyses.

4.2 Performance Hypotheses

4.2.1 Hypothesis for the Primary Endpoint

The null and alternative hypotheses for the primary endpoint are:

$$H_0: \mu_{centurion_Bal\ CDE} \geq \mu_{Infiniti_MFK\ CDE}$$

$$H_A: \mu_{centurion_Bal\ CDE} < \mu_{Infiniti_MFK\ CDE}$$

$\mu_{centurion_Bal\ CDE}$ and $\mu_{Infiniti_MFK\ CDE}$ are the true mean values of the primary endpoint, CDE under Centurion® with the Balanced tip, and Infiniti® with the MFK tip, respectively.

4.2.2 Hypothesis for the Secondary Endpoints

The null and alternative hypotheses for the secondary analyses are:

Secondary hypotheses 1

$$H_0: \mu_{\text{centurion_Bal CDE}} \geq \mu_{\text{centurion_MFK CDE}}$$

$$H_A: \mu_{\text{centurion_Bal CDE}} < \mu_{\text{centurion_MFK CDE}}$$

Where $\mu_{\text{centurion_Bal CDE}}$ and $\mu_{\text{centurion_MFK CDE}}$ are the true mean values of the secondary endpoint, CDE under Centurion® with the Balanced tip, and Centurion® with the MFK tip, respectively.

Secondary hypotheses 2

$$H_0: \mu_{\text{centurion_Bal BSS}} \geq \mu_{\text{Infiniti_MFK BSS}}$$

$$H_A: \mu_{\text{centurion_Bal BSS}} < \mu_{\text{Infiniti_MFK BSS}}$$

Where $\mu_{\text{centurion_Bal BSS}}$ and $\mu_{\text{Infiniti_MFK BSS}}$ are the true mean values of the secondary endpoint, BSS under Centurion® with the Balanced tip, and Infiniti® with the MFK tip, respectively.

Secondary hypotheses 3

$$H_0: \mu_{\text{centurion_MFK BSS}} \geq \mu_{\text{Infiniti_MFK BSS}}$$

$$H_A: \mu_{\text{centurion_MFK BSS}} < \mu_{\text{Infiniti_MFK BSS}}$$

Where $\mu_{\text{centurion_MFK BSS}}$ and $\mu_{\text{Infiniti_MFK BSS}}$ are the true mean values of the secondary endpoint, BSS under Centurion® with the MFK tip, and Infiniti® with the MFK tip, respectively.

Secondary hypotheses 4

$$H_0: \mu_{\text{centurion_MFK CDE}} \geq \mu_{\text{Infiniti_MFK CDE}}$$

$$H_A: \mu_{\text{centurion_MFK CDE}} < \mu_{\text{Infiniti_MFK CDE}}$$

Where $\mu_{\text{centurion_MFK CDE}}$ and $\mu_{\text{Infiniti_MFK CDE}}$ are the true mean values of the secondary endpoint, CDE under Centurion® with the MFK tip, and Infiniti® with the MFK tip, respectively.

[figure not shown]
4.3 Statistical Methods for Performance Analyses

4.3.1 Primary Performance Endpoint

The difference of CDE between two groups will be examined by using an analysis of covariance model (ANCOVA) adjusting for site and baseline opacity grade. Display of ANCOVA results in summary tables will contain difference between LS means, a one-sided p-value < 0.05 will conclude superiority of Centurion over Infiniti group.

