### **Primary:**

The primary hypothesis is to demonstrate that the Centurion® Vision System used with the 45° Balanced Tip will result in less Cumulative Dissipated Energy (CDE) than the Infiniti® Vision System used with the 45° Mini Flared tip during cataract extraction surgery via phacoemulsification:

 $H_o$ :  $\mu_{centurion \ Bal \ CDE} \ge \mu_{lnfiniti \ MFK \ CDE}$ 

 $H_A$ :  $\mu_{centurion Bal CDE} < \mu_{Infiniti MFK CDE}$ 

 $\mu_{centurion\_Bal\ CDE}$  and  $\mu_{Infiniti\_MFK\ CDE}$  are the true mean values of the primary performance endpoint, CDE under Centurion with the Balanced Tip, and Infiniti with the Mini Flared Kelman (MFK) tip, respectively.

The difference of CDE between two groups will be examined by using an analysis of covariance model (ANCOVA) adjusting for site and baseline opacity grade. Display of ANCOVA results in summary tables will contain difference between LS means, a one-sided p- value < 0.05 will conclude superiority of Centurion® over Infiniti® group.

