# 9.3 Rationale for Study Design

The Centurion® Vision System incorporates Active Fluidics™ control system that maintains a stable surgical IOP despite variations in aspiration flow rate. A more stable surgical IOP allows the surgeon to experience less movement of ocular structures, as well as safely lower the surgical IOP. This coupled with the higher resistive aspiration tubing coupled with lower compliant aspiration tubing and Active Fluidics™ minimize occlusion break surge. The

Document: TDOC-0050176 Version: 2.0; Effective; CURRENT

Status: Effective Page 29 of 75

system is capable of creating significantly higher vacuum levels (~20% higher than the Infiniti® Vision system) which creates higher tip holding forces.

Previous Alcon-sponsored study (M-13-006, Data on File) have also shown that the Centurion with the 45° Balanced u/s tip used significantly less CDE than the Infiniti with the 45° MFK tip. At 100% amplitude, the Balanced tip creates 190  $\mu$ m stroke vs 130  $\mu$ m stroke for the MFK tip. The Centurion amplitude is normally set at 60% max and the Infiniti at ~90% max. CDE is therefore reduced by 33%.

This study has been designed to obtain a better understanding of how both the Centurion® and the Balanced Tip affect CDE and BSS fluid used, as well as assess the correlation to  $\Delta$ CCT and  $\Delta$ ECD.

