### 11.1 Investigational Products

The Centurion® Vision System and Infiniti® Vision System, including accessories approved by Alcon (ie, tips, sleeves and packs, etc), constitute complete surgical systems. These systems are intended for use by licensed ophthalmic surgeons and their surgical teams. The Vision System devices utilized in this postmarket trial are CE Marked and 510k cleared. Approved labeling will be applied and devices provided in standard manufacturer's packaging (where applicable).

**Test Article:** Centurion® Vision System (v2.04) will be used with the 45° Balanced Tip (coupled with the INTREPID® Ultra Infusion sleeve).

The Centurion® Vision System is a phacoemulsification aspiration platform indicated for emulsification, separation, and aspiration of cataracts, residual cortical material and lens epithelial cells; vitreous aspiration and cutting associated with anterior vitrectomy; bipolar coagulation; and intraocular lens injection. The system employs similar functionality and technologies of its predecessor, the Infiniti® Vision System. In addition to the existing functions for irrigation/aspiration, phacoemulsification, vitreous aspiration cutting, and bipolar coagulation, the CVS also introduces new modalities for active irrigation, automated IOL injection, and advanced surgical display for viewing of biometry data and surgical operating parameters.

Standard, sterile, single-use pack of supplies and accessories necessary to perform one cataract removal procedure each will be locally procured by the investigational sites (Alcon will reimburse the costs).

<sup>1Used with INTREPID® Ultra Infusion Sleeve

[figure not shown]
<sup>2Used with Ultra infusion Sleeve

**Document:** TDOC-0050176 Version: 2.0; Effective; CURRENT

Status: Effective Page 33 of 75

See Figure 11-1 and Figure 11-2 for product and accessory diagrams.

Figure 11–1 Test Article Diagram

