5.4 Interim Analysis for Safety

Not Applicable.

6 Sample Size and Power Calculations

Based on previous studies, a sample size of 53 subjects in each procedure group will have a 80% power to detect a mean difference of -7.4 percent-seconds in CDE between the two procedure groups (Centurion® with the 45° Balanced tip minus Infiniti® with the MFK tip) using a two-sample t-test with a one-sided 5% level of significance, assuming a common standard deviation of 15.2.. Assuming a 10% dropout rate, 59 subjects per procedure group (up to 177 in total) will be randomized.

7 References

See protocol Section 17 for details.

8 Revision History

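### Does the primary conclusion claim too much by saying Centurion beats Infiniti without naming the tip?

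*SAP*

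**What the plan says.** The three arms (protocol 9.1, SAP 1.2) are Centurion with the Balanced tip (Arm 1), Centurion with the MFK tip (Arm 2) and Infiniti with the MFK tip (Arm 3). Both Centurion arms carry the footnote "Used with INTREPID® Ultra Infusion Sleeve"; the Infiniti arm uses the Ultra sleeve.

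The primary hypothesis in SAP 4.2.1 compares mean "CDE under Centurion® with the Balanced tip, and Infiniti® with the MFK tip, respectively". Protocol 15.4.1.1 states the same hypothesis.

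The sentence that draws the conclusion is shorter. SAP 4.3.1 says "a one-sided p-value < 0.05 will conclude superiority of Centurion over Infiniti group". The protocol synopsis has "value < 0.05 will conclude superiority of Centurion® over Infiniti® group", and protocol 15.4.1.2 repeats it. None of the three names a tip.

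The Decision Criteria in the SAP Executive Summary first identify the two groups correctly, then say that a small p-value shows that the "CDE for Centurion® with the 45° Balanced MFK tip is statistically significantly less than the CDE for Infiniti® with the MFK tip".

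Secondary hypothesis 1 compares the two tips on Centurion. Secondary hypothesis 4 compares mean "CDE under Centurion® with the MFK tip, and Infiniti® with the MFK tip, respectively", so it holds the tip constant.

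**The concern.** Because Arms 1 and 2 are both Centurion arms, the words Centurion group do not by themselves identify the tested arm. Arm 1 also differs from Arm 3 in three components at once, so a significant primary test supports one configuration over another and does not isolate the console. Protocol 9.3 says the trial is meant to show how both the console and the tip affect CDE, and a conclusion that credits only the console seems to undo that separation.

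The CDE formula adds to the worry. In protocol 8.4.1 torsional CDE is proportional to average torsional amplitude, and protocol 9.3 says: "The Centurion amplitude is normally set at 60% max and the Infiniti at ~90% max". Part of any CDE difference may therefore follow from tip and amplitude. Finally, the SAP success paragraph names a tip that does not exist in the trial. If these sentences governed the analysis or the report, the wrong arms could be compared or a console effect could be claimed from a contrast that does not show one.

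**Working it through.** **1. Which arms does each statement identify?**

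| Place | Active side | Control side |
|---|---|---|
| Primary objective (protocol 8.1, SAP 1.1) | Centurion, Balanced tip | Infiniti, MFK tip |
| Primary hypothesis (synopsis, protocol 15.4.1.1, SAP 4.2.1) | Centurion, Balanced tip | Infiniti, MFK tip |
| Sample size (SAP 6) | Centurion, Balanced tip | Infiniti, MFK tip |
| SAP Executive Summary, key objective and endpoint paragraph | Centurion, Balanced tip | Infiniti, MFK tip |
| SAP Executive Summary, last sentence of Decision Criteria | Centurion, merged tip name | Infiniti, MFK tip |
| Conclusion sentence (synopsis, protocol 15.4.1.2, SAP 4.3.1) | Centurion, tip not named | Infiniti, tip not named |

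The first four rows agree. The fifth contains the word Balanced, which applies only to Arm 1, and follows a correct definition of the two groups. The sixth closes a paragraph that opens by referring to the CDE difference between two groups, and those groups are defined in the hypothesis just before it. No statement identifies a different pair of arms, and no section plans to pool Arms 1 and 2.

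**2. Does the stated sample size belong to this contrast?**

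Inputs: difference 38.5 − 45.9 = −7.4 (protocol 15.10), "assuming a common standard deviation of 15.2" (SAP 6), one-sided alpha 0.05, power 80%, equal groups.

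- n per group = 2 × SD² × (z₀.₉₅ + z₀.₈₀)² / difference² = 2 × 15.2² × (1.645 + 0.842)² / 7.4² ≈ 52.2, rounded up to 53.
- Exact noncentral-t power is 80.1% at 53 per group and 79.4% at 52.
- Dropout: 53 / 0.90 = 58.9, rounded up to 59 per group; 3 × 59 = 177.

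The plan's 53, 80%, 59 and 177 all reproduce for Arm 1 against Arm 3.

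**3. What if Centurion group were read as both Centurion arms?**

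That would compare 106 subjects with 53. Power would then depend on the CDE reduction in Arm 2 relative to Infiniti, which the documents do not give. With the other inputs unchanged:

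| Assumed Arm 2 reduction | Pooled difference | Power |
|---|---|---|
| 0 | (7.4 + 0)/2 = 3.70 | 42% |
| 3.7 | (7.4 + 3.7)/2 = 5.55 | 70% |
| 7.4 | (7.4 + 7.4)/2 = 7.40 | 89% |

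Only the two-arm reading gives the stated 80% from the stated inputs without a further assumption. SAP 6 also names the two arms of the difference.

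**4. How often would the primary succeed without support for the console?**

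The primary effect is the sum of two secondary effects: (Arm 1 − Arm 3) = (Arm 1 − Arm 2) + (Arm 2 − Arm 3), that is, secondary 1 plus secondary 4. The split of 7.4 is not documented, so a range is assumed. The joint figures come from 400,000 simulated three-arm trials with plain t-tests, 53 per arm and SD 15.2.

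| Console-plus-sleeve share of 7.4 | Stand-alone power, secondary 4 | Primary significant, secondary 4 not |
|---|---|---|
| 0% (0) | 5% | 75% |
| 25% (1.85) | 15% | 65% |
| 50% (3.70) | 34% | 48% |
| 75% (5.55) | 59% | 27% |

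These figures describe the power of secondary 4 and would be identical if every sentence named the tips. They use t-tests, where the plan uses ANCOVA with site and opacity grade, and they set aside the sequential testing order. They do not measure any effect of the wording.

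**The case for a change.** The strongest case for a change is that these sentences are decision rules: one stands under the criteria for study success and the others state what a positive test concludes. The trial has Arm 2 so that tip and console can be separated, and step 4 shows that a significant primary without a significant secondary 4 is a common outcome under the planned inputs. A report that copied the short sentence could then credit the console without support, and naming the tips costs a few words.

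The looseness of the wording stands, as does the tip-name slip. The consequence does not follow. To report a console effect from SAP 4.3.1, a reader would have to ignore the hypothesis before it, the objective and the sample size section. If secondary 4 fails, the correctly worded primary claim for Arm 1 remains. Subject to the testing sequence, so do the tip comparison in secondary 1 and the two fluid-use comparisons with Infiniti in secondaries 2 and 3, the latter with the same tip. In the simulations secondary 1 was also significant in 0.485 of the 0.652 at a 25% share, and in 0.269 of the 0.478 at a 50% share.

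A rule that tip effects come only from secondary 1 and console-plus-sleeve effects only from secondary 4 would repeat what those hypotheses already say. A table of amplitude by arm is a separate, optional idea. The metrics and supportive endpoints are partly redacted, protocol 15.4.3.1 already plans descriptive statistics for supportive endpoints, and protocol 12.1.2.5 has altered machine settings recorded. It cannot be shown that such a summary is missing.

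**Conclusion.** No change follows. The conclusion sentence is an abbreviation and the merged tip name is a clerical slip; the surrounding text resolves both to Arm 1 against Arm 3 on CDE. The effect on the test, one-sided alpha of 0.05, 53 per group, 80% power and 177 randomized is zero. The primary result should be read as a comparison of two configurations, with tip and console taken from secondaries 1 and 4, and the plan's own objectives already support that reading.

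This rests on the analysis following the stated hypothesis, which is the only contrast that both documents define for the primary endpoint. The low power of secondary 4 in step 4 depends on an assumed split of the 7.4 and is a separate matter from the wording.
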